## 6.12. Safety Analyses

Percentages will be calculated using the Safety populations as the denominator. For events that are sex-specific, the denominator and computation of the percentage will include only participants from the given sex. In the event of differential dropout rates, additional summary tables comparing exposure-adjusted incidence rates will be generated instead of, or in addition to, percentages.

Generally, the following statistical methods will be used, unless otherwise noted:

- percentage-based analyses:
  - p-values based on Fisher's exact test, and
  - odds ratios with treatment as the numerator and placebo as the denominator
- continuous measurements (single postbaseline timepoint):
  - p-value based on ANCOVA:
    - model containing terms for treatment and the continuous covariate of baseline measurement, and
    - Type III sums of squares will be used.
- continuous measurements (multiple postbaseline timepoints):
  - p-value based on MMRM:
    - model containing terms for treatment, visit, the continuous covariate of baseline measurement, and the interactions of treatment by visit, and
    - Type III sums of squares will be used.

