6.3. Measures to Minimize Bias: Randomization and Blinding

Randomization

Participants who meet all criteria for enrollment will be randomized on Day 1 as follows:

- In Part 1, 1:1 to double-blind treatment
- In Part 2, will be allocated as follows:
 - Prevention Cohort: 1:1:1 to double blinded treatment
 - Treatment Cohort: 1:1, as described in Part 2 Treatment Cohort below
- In Part 3, 1:1 to open label treatment

To achieve between-group comparability, block randomization within each facility will be used. Randomized participants within the facility will be stratified by role within the facility (resident versus facility staff), by sex, and whether or not the participant received a SARS-CoV-2 vaccine prior to screening (in Part 3 only).

All participants will be centrally randomized to study intervention using an Interactive Web Response System (IWRS). Before the study is initiated, the log in information and directions for the IWRS will be provided to each site.

Blinding

Part 1 and Part 2 Prevention Cohort

Part 1 and Part 2 are blinded. Neither participants, nor investigators, nor the sponsor study team will be aware of treatment assignments prior to the final database locks at the conclusion of the study, except as described in the following note.

Note: It is possible that some participants will have the SARS-CoV-2 negative result on the screening point of care test, but could be positive on the baseline SARS-CoV-2 PCR test. The results from the baseline PCR test will not be available until after the participant is randomized. Once positive results are known from the baseline PCR test, these participants will be unblinded and have the option to continue to be followed for safety according to the Prevention Cohort SoA. This table describes general procedures for unblinding.

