**Table PYAD.6.3. Tables and Figures Related to Demographics and Other Characteristics of Study Population**

Method	Analysis
Descriptive Statistics	Number of participants, mean, standard deviation, median, minimum, maximum, and 10 th and 90 th percentiles for continuous measures, and frequency counts and percentages for categorical measures
Kaplan-Meier curves and summary statistics, Cox proportional hazards	Treatment comparisons of time-to-event based endpoints
Logistic regression analysis	Treatment comparisons of binary variables with treatment, facility, and randomization stratification variables in the model

Nonparametric (e.g., Mann-Whitney or van Elteren tests)	Treatment comparison of ordinal, nominal, and non-normally distributed continuous variables
Mixed-effects model repeated measures (MMRM) analysis	Treatment comparisons of continuous efficacy and health outcome variables
Chi-square test or Fisher's exact test	Treatment comparison of binary endpoints

Treatment comparisons of continuous safety variables with multiple postbaseline measurements will be made using MMRM analysis. When MMRM is used, it includes: (a) treatment group, (b) facility, (c) role within the facility (resident vs staff), (d) sex, (e) baseline value in the model, (f) visit, and (g) the interactions of treatment-by-visit as fixed factors, and the patient as a random effect. The covariance structure to model the within-patient errors will be unstructured. If the unstructured covariance matrix results in a lack of convergence, the heterogeneous Toeplitz covariance structure, followed by the heterogeneous autoregressive covariance structure, will be used. The first structure to yield convergence will be used for inference. The Kenward-Roger method will be used to estimate the denominator degrees of freedom. Type III sums of squares for the least-squares (LS) means will be used for the statistical comparison; the 95% confidence interval (CI) will also be reported. Unless otherwise specified, for MMRM, reported data from only planned visits will be used as the primary analysis.

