Treatment comparisons of continuous efficacy and safety variables with a single postbaseline timepoint will be made using analysis of covariance (ANCOVA) with: (a) treatment group, (b) facility, (c) role within the facility (resident vs staff), (d) sex and (e) baseline value in the model. Type III sums of squares for LS means will be used for statistical comparison between treatment groups. The LS mean difference, standard error, p-value-, and 95% CI, unless otherwise specified, will also be reported. Missing data imputation method for the ANCOVA model is specified in Section 6.3.

Treatment comparisons for binary efficacy endpoints will be made using logistic regression. The model will include the treatment groups, facility, and the stratification factors (resident/staff and sex) as explanatory variables. For the primary and key secondary endpoints, p-values from Rao's score test (or score test) will be reported (Rao 1948). For all other endpoints, results from a Wald test will be reported. The odds ratio and the corresponding CIs, as well as the treatment differences and the corresponding CIs, will be reported.

For other binary endpoints, treatment comparisons will be made using Chi-square tests if the expected count is at least 5 in at least 80% of the cells, otherwise a Fisher's exact Test will be used.

The Kaplan-Meier (KM) product limit method will be used for time-to-event analyses. The hazard ratio and log-rank test will be reported. Time for all analyses will be described in units of days.

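### SAP 6.1.4 and SAP 6.12 give different models for the same continuous safety variables, so the safety p-values are not uniquely pre-specified

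*SAP*

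**What the plan says.** **SAP 6.1.4, several postbaseline values.** Below Table PYAD.6.3 the text reads: "Treatment comparisons of continuous safety variables with multiple postbaseline measurements will be made using MMRM analysis". It then lists the terms: "When MMRM is used, it includes: (a) treatment group, (b) facility, (c) role within the facility (resident vs staff), (d) sex", followed by baseline, visit, treatment-by-visit and a patient random effect.

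**SAP 6.1.4, one postbaseline value.** "Treatment comparisons of continuous efficacy and safety variables with a single postbaseline timepoint will be made using analysis of covariance (ANCOVA) with" treatment, facility, role, sex and baseline.

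**SAP 6.12.** The safety MMRM is a "model containing terms for treatment, visit, the continuous covariate of baseline measurement, and the interactions of treatment by visit". The safety ANCOVA is a "model containing terms for treatment and the continuous covariate of baseline measurement". Facility, role and sex appear in neither. The list is introduced as a general default that other text may override.

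**Protocol.** Section 9.4.1 gives an MMRM without facility, role or sex, names only the baseline value as covariate for ANCOVA, and assigns continuous laboratory measurements to ANOVA on ranks. Section 9.4.8 covers vital signs and laboratory analytes and analyses continuous safety measures by MMRM, naming treatment as the only term.

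**Randomization.** Protocol 6.3 uses blocks within each facility: "Randomized participants within the facility will be stratified by role within the facility (resident versus facility staff), by sex", with vaccine status added in Part 3.

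**Percentages.** SAP 6.12 names only Fisher's exact test. For binary endpoints outside the efficacy models, SAP 6.1.4 says "treatment comparisons will be made using Chi-square tests if the expected count is at least 5 in at least 80% of the cells", and Fisher otherwise. Protocol 9.4.1 has the same expected-count rule. Protocol 9.4.6.1 and 9.4.8 name chi-square or Fisher for safety without saying when each applies.

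**The concern.** Two analysts following this SAP could fit different models to the same vital-sign or laboratory variable and report different p-values, each with a section to cite. The choice could also be made after the data are seen. Actual outputs depend on it. Table PYAD.6.9 attaches an ANCOVA p-value to change from baseline without saying which ANCOVA, and promises statistical comparisons for the shift tables without naming a test.

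The two models also behave differently. Allocation was balanced on facility, role and sex. If those factors predict the outcome, balancing on them makes the arm difference more precise, but a model that leaves them out returns their variance to the error term. The reported standard error is then too large and the test rejects less often than its nominal level. For a safety comparison, that means some loss of power to detect a difference.

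**Working it through.** The documents state no sample size, power or error rate for safety, so there is no safety figure to reproduce. The check has three steps.

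**1. The specifications side by side**

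| Variable | SAP 6.1.4 | SAP 6.12 | Protocol |
|---|---|---|---|
| Continuous, several postbaseline values | MMRM with facility, role, sex | MMRM without them | 9.4.1: MMRM without them; 9.4.8: MMRM, treatment named |
| Continuous, one postbaseline value | ANCOVA with facility, role, sex | ANCOVA, treatment and baseline | 9.4.1: ANCOVA, baseline as covariate |
| Continuous laboratory values | as above | as above | 9.4.1: ANOVA on ranks; 9.4.8: MMRM |
| Percentages | chi-square or Fisher by expected count | Fisher only | 9.4.1: expected-count rule; 9.4.6.1 and 9.4.8: either test |

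**2. Effect of leaving out the randomization factors**

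Let R² be the share of outcome variance, among what remains after baseline, that facility, role and sex explain. The documents do not give it, so a range is assumed. With the factors balanced by design, the reported standard error is too large by 1/√(1−R²). For a two-sided 0.05 test:

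- true size = 2Φ(−1.96/√(1−R²))
- power, where the adjusted test has 80% = Φ(1.96 + 0.842 − 1.96/√(1−R²))

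At R² = 0.10: 1.96/√0.90 = 2.066, so size = 2Φ(−2.066) = 0.039 and power = Φ(0.736) = 76.9%.

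| R² (assumed) | SE too wide by | True size | Power (adjusted = 80%) |
|---|---|---|---|
| 0 | 0% | 0.050 | 80.0% |
| 0.02 | 1.0% | 0.048 | 79.4% |
| 0.05 | 2.6% | 0.044 | 78.5% |
| 0.10 | 5.4% | 0.039 | 76.9% |
| 0.20 | 11.8% | 0.028 | 72.9% |

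A simulation with 1700 participants, an assumed 80 facilities and 1500 runs per setting gave the same pattern. At R² of 0.05, 0.10 and 0.20 the unadjusted size was 0.042, 0.039 and 0.023, against 0.051, 0.048 and 0.045 when adjusted. Power was 0.791, 0.781 and 0.705, against 0.799, 0.806 and 0.789. The Monte Carlo standard error is about √(0.05×0.95/1500) = 0.006 for size and √(0.8×0.2/1500) = 0.010 for power.

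**3. Fisher alone against the expected-count rule**

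In a 2×2 table, 80% of four cells is 3.2, so the rule requires all four expected counts to be at least 5. Part 1 randomizes about 1700 participants 1:1, or 850 per arm. With equal arms, chi-square then needs at least 10 events in total. The event rates below are assumed, and the results come from exact binomial enumeration at two-sided 0.05.

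| Rates, 850 per arm | Fisher | Rule |
|---|---|---|
| 0.2% both (size) | 0.003 | 0.003 |
| 1% both (size) | 0.028 | 0.048 |
| 5% both (size) | 0.039 | 0.049 |
| 0.5% vs 2% (power) | 0.763 | 0.831 |
| 1% vs 2.5% (power) | 0.596 | 0.674 |
| 2% vs 4% (power) | 0.634 | 0.688 |
| 20% vs 25% (power) | 0.675 | 0.696 |

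The power difference runs from about 2 to 8 points. It is of similar size at 567 per arm (1700/3, the Part 2 Prevention Cohort). At 0.2% the expected total is 1700 × 0.002 = 3.4 events. The rule then uses Fisher in 99.7% of tables and the two approaches coincide.

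**The case against.** **The protocol agrees with 6.12.** A reader might infer that 6.12 drops covariates the plan requires. The documents do not support that. The protocol 9.4.1 MMRM lacks the same three terms, and 6.1.4 is the section that adds them. This stands: the finding is an unreconciled conflict, and the documents do not say which side is right.

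**The adjusted MMRM may be meant for efficacy.** The MMRM row of Table PYAD.6.3 refers to efficacy and health outcome variables. But the text directly below it names safety variables, and the ANCOVA sentence names both, so this does not remove the conflict.

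**6.12 is only a default, or is the more specific section.** Its opening qualifier could be read as deferring to 6.1.4, and its place in the safety section as overriding it. Both readings are available, which is the problem.

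**The conservatism is conditional.** Both 6.12 models adjust for baseline, which may absorb most of the difference between residents and staff. This stands. The loss can be zero, and no document gives the residual share.

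**Harm detection does not rest on these p-values.** A reader might infer that the plan would miss harm. That goes too far. No safety comparison is powered, and safety tests are run at 0.05 without multiplicity adjustment (SAP 6.1.4 and 6.5). The plan also has odds ratios, death and event listings, narratives for deaths, SAEs and discontinuations due to adverse events (SAP 6.12.4), and monthly DSMB review of unblinded data (SAP 6.15.1).

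**Fisher alone is defensible.** Protocol 9.4.6.1 and 9.4.8 allow either test, and many adverse-event tables are sparse. This stands: calling it an error is not supported.

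**Fixed facility effects may not fit in Part 3.** Part 3 may have as few as 30 participants, and it is also stratified by vaccine status. This stands and shapes the fix.

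**Conclusion.** The conflict over model terms is real and should be settled. SAP 6.1.4 and 6.12 prescribe different ANCOVA and MMRM models for the same continuous safety variables. The protocol agrees with 6.12 on the MMRM and offers ANOVA on ranks as a third method for laboratory values.

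If 6.12 is followed, the cost is small to moderate: about 1 to 3 power points if the randomization factors explain 2% to 10% of the variance left after baseline, about 7 points at 20%, and none at 0%. These figures assume good balance on the factors and a variance share that the documents do not report. They support a claim of modestly reduced power for continuous safety measures, and not a claim that harm would go undetected.

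The percentage test is a consistency point only. Fisher alone is permissible but conservative, and the choice hardly matters for the rarest events.

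**What to change.** In SAP 6.12:

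- **Parts 1 and 2.** Replace the two model lines with the 6.1.4 models. ANCOVA: treatment, facility, role, sex, baseline. MMRM: the same plus visit and treatment-by-visit, with the 6.1.4 within-patient structure.
- **Part 3.** Use its own stratification factors (role, sex, vaccine status) with treatment and baseline. Omit or pool facility when it is too sparse, with the criterion written down in advance.
- **Protocol.** State that these terms replace those of the protocol 9.4.1 MMRM, and give the reason: the analysis should reflect the randomization. Say whether continuous laboratory values follow these models or the ANOVA on ranks.
- **Percentages.** State one rule, either Fisher throughout or the expected-count rule, and use it in 6.1.4, 6.12 and the shift tables.

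Make the choice before the data concerned are unblinded. The cost is SAP wording and a recorded justification. Protocol 9.4 places changes that do not alter a principal feature in the SAP and CSR, so an amendment should not be needed if safety model terms are regarded as falling below that level. Facility, role and sex are already in the efficacy models, and prior vaccination is already collected at screening.

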### 6.12.1. Baseline and Postbaseline Definitions for Safety Groups

Table PYAD.6.7 provides conceptual definitions of baseline and postbaseline by analysis type. More specific detail for each submission is provided in an appendix, if necessary.

**Table PYAD.6.7. Baseline and Postbaseline Definitions for Safety Groups  
Initial Controlled Periods of Individual Studies  
Controlled Integrated Analysis Sets**

Analysis Type	Baseline	Postbaseline
TEAEs	Start of screening and ends prior to the study drug dose.	Starts after initiation of the study drug dose and ends on or prior to the day of study disposition
Treatment-Emergent Abnormal Laboratory Values and Vital Signs	Start of screening and ends prior to the study drug dose.  All scheduled and unscheduled measurements will be included.	Starts after initiation of the study drug dose and ends on or prior to the day of study disposition.  All scheduled and unscheduled measurements will be included.

**Baseline and Postbaseline Definitions for Safety Groups****Initial Controlled Periods of Individual Studies****Controlled Integrated Analysis Sets**

Analysis Type	Baseline	Postbaseline
Change from Last Baseline to Week xx and to Last Postbaseline for Laboratory Values and Vital Signs	Start of screening and ends prior to the study drug dose.  The last scheduled nonmissing assessment recorded prior to the date of the first dose.	Starts after initiation of the study drug dose and ends on or prior to the day of study disposition.
		Only scheduled visits will be included. The early termination visits are considered scheduled visits.

Abbreviation: TEAE = treatment-emergent adverse event.

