Urine pregnancy	X	X										X		X		Only for WOCBP (Section 10.4, Appendix 4) Local laboratory. Test performed in the 24 hours prior to study entry will be accepted for determination of eligibility. No samples needed if participant is hospitalized.*
Hematology		X			X				X	X	X	X				Day 1: pre-dose. Assayed by Lilly-designated laboratory No samples needed if participant is hospitalized.*
Clinical Chemistry		X			X				X	X	X	X				Day 1: pre-dose. Assayed by Lilly-designated laboratory No samples needed if participant is hospitalized.*
LDH		X							X	X						Day 1: pre-dose. Assayed by Lilly-designated laboratory No samples needed if participant is hospitalized.*

Procedures	Screening	Evaluation Period										ETV	Post-Evaluation Follow-Up			Comments
Study Day	Max 7-day window	1	2-7	8	15	22	29	36	43	50	57		85	141	169	
Visit window (± number of days)	--	--	--	2	2	2	2	2	2	2	2		7	7	7	

 • C-reactive protein; high-sensitivity • Ferritin • D-dimer • Procalcitonin • Troponin 		X										X	X			Day 1: pre-dose. Assayed by Lilly-designated laboratory No samples needed if participant is hospitalized.*
PK sample		X					X					X	X	X	X	Day 1: pre-dose. For participants in Part 2, Day 1 collection is post-dose only (approx. 30 minutes after end of infusion). Assayed by Lilly-designated laboratory No samples needed if participant is hospitalized.*
Immunogenicity (ADA) sample		X					X					X	X	X	X	Day 1: pre-dose. Remaining days: Collect with time-matched PK sample. No samples needed if participant is hospitalized.*
Exploratory biomarker samples		X					X					X	X	X	X	Day 1: pre-dose Assayed by Lilly-designated laboratory No samples needed if participant is hospitalized.*
Pharmacogenetics sample		X														Assayed by Lilly-designated laboratory

Abbreviations: ACVPU = alert, confusion, voice, pain, unresponsive; ADA = antidrug antibody; AE = adverse event; BP = blood pressure; COVID-19 = coronavirus disease – 2019; FiO2 = fraction of inspired oxygen in the air; ETV = early termination visit; FiO2 = fraction of inspired oxygen; ICU = intensive care unit; IV = intravenous; LDH = lactate dehydrogenase; NSAID = nonsteroidal anti-inflammatory drug; PCR = polymerase chain reaction; PK = pharmacokinetic; POC = point of care; SpO2 = saturation of peripheral oxygen; SARS-CoV-2 = severe acute respiratory syndrome coronavirus 2; WOCBP = women of child-bearing potential

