9.4.1. General Considerations

Baseline values for all measurements will be the last measurement taking prior to receiving study intervention, unless otherwise specified.

The primary analyses of the primary endpoints and key secondary endpoints will be based on events that occurred after randomization.

The analysis model for time-to-event analyses will be a Cox proportional hazards regression model for the time to the first occurrence of the relevant event, with treatment as a fixed effect. For continuous measures, analysis of covariance (ANCOVA) and/or mixed-effects model for repeated measures (MMRM) will be used to analyze changes from baseline with the baseline

value as the covariate. The MMRM model will include fixed effects for treatment, visit, treatment-by-visit interaction, the baseline as a covariate and the participant as a random effect. Summary statistics will include sample size, mean, standard deviation, median, 10th and 90th percentiles for both the actual and the change from baseline measurements. Least-squares mean (LS mean) and standard error derived from the model will also be displayed for the change from baseline measurement. Treatment comparisons will be displayed showing the treatment difference LS Mean and the 95% confidence limits along with the p-value.

For continuous lab measurements, an analysis of variance (ANOVA) on ranks will be used and p-values for the difference between each study intervention and placebo will be reported.

For categorical measures, summary statistics will include sample size, frequency, and percentage. For primary and secondary analyses, a logistic regression model will be used. The model will include fixed effects for treatment and stratification factors such as facility. For other analyses, frequencies will be analyzed using Chi-square tests if the expected count is at least 5, in at least 80% of the cells, otherwise a Fisher's exact Test will be used.

All analyses will be implemented using SAS[®] Version 9.4 or higher, or R version 3.6.3 or higher.

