### **6.1.2. Definition of Study Baseline**

Unless otherwise specified, for all measurements, baseline is defined as the last nonmissing assessment recorded on, or prior to, the date of the study drug administration at study Day 1.

Baseline SARS-CoV-2 RT-PCR and serology status will be based on evaluable test results on, or prior to, the date of study drug administration at study Day 1. A participant will be considered RT-PCR positive at baseline if any RT-PCR result is determined to be positive.

Baseline for safety analysis is described in the safety section.

Change from baseline will be calculated as the visit value of interest minus the baseline value. If a baseline value or the value at the visit is missing for a particular variable, then the change from baseline is defined as missing.

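### The change-from-baseline row of SAP Table PYAD.6.7 cuts off at the date of first dose, which read literally excludes the Day 1 pre-dose sample, the only scheduled laboratory baseline

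*SAP*

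**What the plan says.** SAP 6.1.2 gives a general rule that includes the dosing date: "baseline is defined as the last nonmissing assessment recorded on, or prior to, the date of the study drug administration at study Day 1". It then hands safety over to another section, "Baseline for safety analysis is described in the safety section", and says that if the baseline or visit value is absent, "then the change from baseline is defined as missing".

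The safety definitions are in SAP 6.12.1, Table PYAD.6.7. The third row covers change from last baseline for laboratory values and vital signs. Its baseline cell has two sentences. The first sets the period: "Start of screening and ends prior to the study drug dose". The second picks the value within it: "The last scheduled nonmissing assessment recorded prior to the date of the first dose". The other two rows of the table (adverse events and treatment-emergent abnormalities) use only the first cut-off, at the dose.

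Protocol 9.4.1 says: "Baseline values for all measurements will be the last measurement taking prior to receiving study intervention, unless otherwise specified".

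In both SoAs (protocol 1.3.1 and 1.3.2), the comment on the hematology and chemistry rows is "Day 1: pre-dose. Assayed by Lilly-designated laboratory", and the screening column for these rows is blank. The infusion is also on Day 1. Protocol 1.3 allows screening and Day 1 procedures on the same day.

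These baselines feed planned analyses. Protocol 9.4.8 plans mean change by visit with an MMRM for continuous safety measures, covering vital signs and laboratory analytes. SAP 6.12 puts the baseline measurement in its safety ANCOVA and MMRM models.

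**The concern.** One cell holds two different cut-offs. The first sentence ends the baseline period at the dose, so a Day 1 pre-dose sample lies inside it. The second stops before the calendar date of the dose, so the same sample lies outside. The second sentence is the one that selects the value, so a programmer working to the letter would apply it.

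For the laboratory tests nothing can take the sample's place. No screening draw is scheduled, and because the sentence accepts only scheduled assessments, an earlier unscheduled sample cannot be used either. With no baseline the change is missing, and the models that need baseline as a covariate have no observations. At stake is the planned laboratory change-from-baseline summary in all three parts and, to an unknown extent, the one for vital signs.

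**Working it through.** The plan gives no figure to reproduce. The check takes each scheduled safety measurement in the two SoAs and asks whether it supplies a baseline under each of three cut-offs:

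- A: before the date of first dose (Table PYAD.6.7, third row, second sentence)
- B: before the dose (same cell, first sentence; also protocol 9.4.1)
- C: on or before the date of dosing (SAP 6.1.2, general rule)

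| SoA | Measurement | Screening | Day 1 | A | B | C |
|---|---|---|---|---|---|---|
| 1.3.1 | Hematology | none | pre-dose | no | yes | yes |
| 1.3.1 | Chemistry | none | pre-dose | no | yes | yes |
| 1.3.1 | LDH | none | pre-dose | no | yes | yes |
| 1.3.1 | CRP, ferritin, D-dimer, procalcitonin, troponin | none | pre-dose | no | yes | yes |
| 1.3.2 | Hematology | none | pre-dose | no | yes | yes |
| 1.3.2 | Chemistry | none | pre-dose | no | yes | yes |
| 1.3.2 | CRP, ferritin, D-dimer, procalcitonin, troponin | none | pre-dose | no | yes | yes |
| both | Vital signs | yes | yes, not timed against infusion | only if screened on an earlier date | yes | yes |

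Section 1.3.1 covers Part 1 and the Part 2 Prevention Cohort; 1.3.2 covers the Part 2 Treatment Cohort and Part 3. LDH has its own row only in 1.3.1.

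Laboratory rows with an eligible scheduled baseline:

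- Under A: 0 of 4 in 1.3.1 plus 0 of 3 in 1.3.2, so 0 of 7.
- Under B: 4 of 4 plus 3 of 3, so 7 of 7.
- Under C: also 7 of 7.

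The result under A follows from the schedule alone and does not depend on the participant. It would therefore apply to everyone: about 1700 randomized in Part 1, about 2000 in Part 2 and 30 to 500 in Part 3.

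For vital signs, A leaves the screening reading, which can be up to 7 days old, when screening precedes Day 1. Any Day 1 reading taken before infusion is passed over. When screening and Day 1 coincide, A leaves nothing. Neither document says how often that happens.

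C is not a clean replacement. Because it works by date, it could admit a Day 1 vital-sign reading taken after the infusion. B avoids this.

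**The case against.** The strongest reply is that the intended rule is plain. The first sentence of the cell, the other rows of the table, protocol 9.4.1 and the SoA's own pre-dose label all point to the Day 1 sample. SAP 6.12.1 calls its definitions conceptual and promises more detail in an appendix if needed. A laboratory change table with no observations would also reveal the error at once.

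Most of this stands, and it limits the point to a wording error. It does not remove it. SAP 6.1.2 explicitly sends safety baselines to this table, and the SAP's only appendix is the NIAID scale, so nothing overrides the sentence. Choosing the intended meaning would mean departing from the written rule. Protocol 9.4.1 does allow other specifications, so the SAP may set its own rule. But a deliberate exception that leaves no laboratory baseline cannot have been the aim.

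Three stronger readings are tempting, and the documents do not support them:

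- *The study has no planned laboratory baseline.* It has one: every participant is scheduled for a Day 1 pre-dose draw. What is missing is a sample that meets this sentence.
- *The safety analysis as a whole is compromised.* Only the change-from-baseline row is affected. SAP 6.12.6 does not itself specify a laboratory change table; the laboratory change analysis comes from protocol 9.4.8 and the general methods in SAP 6.12.
- *Vital-sign changes are materially distorted by an old baseline.* The SoAs do not time Day 1 vital signs against the infusion, and nothing shows that a screening reading up to 7 days old misleads.

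**Conclusion.** The selection sentence is wrong as written and should be fixed. Read literally, it leaves 0 of 7 laboratory rows with an eligible baseline, so laboratory change from baseline would be missing for all participants in all three parts. For vital signs it removes the baseline of those screened and dosed on the same day, a number the documents do not give.

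The size is conditional on the sentence being programmed literally, on Day 1 being the infusion date as scheduled, and on SAP 6.1.2 being applied to the missing baseline. The treatment-emergent abnormality row keeps the Day 1 pre-dose sample, and adverse event and efficacy analyses do not use this rule. No collected data are lost. This is a contradiction to be corrected before programming, not a flaw in the design.

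**What to change.** In the third row of Table PYAD.6.7, replace the date cut-off in the second sentence so that it reads, in substance: *last scheduled nonmissing assessment obtained before the start of the study drug dose (Day 1 pre-dose assessments qualify)*. This agrees with the first sentence of the cell and with protocol 9.4.1.

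The cost is a few words in the SAP. No new samples, visits or analyses are needed. One detail is left for the programming specification: Day 1 vital signs carry no pre-dose label in the SoAs, so a Day 1 reading should count as baseline only if its recorded time is before the start of infusion. The specification should also state how untimed Day 1 readings are handled.
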